Nonmeasurable Lesions:

All other lesions, including small lesions (longest diameter < 10 mm by CT/MRI/ultrasound for nodal/soft tissue disease [including lymph nodes] or < 10 mm caliper measurement by clinical exam for superficial cutaneous melanoma lesion) and

other truly nonmeasurable lesions are considered nonmeasurable and characterized as nonindex lesions. This will include any measurable lesions beyond the maximum number of 10 lesions that were not chosen as index lesions.

Lesions with Prior Local Treatment:

Tumor lesions situated in a previously irradiate area, or an area subject to other loco-regional therapy, are usually not considered measurable unless there has been demonstrated progression in the lesion.

Coalescing or splitting lesions:

- **Coalescing lesions:** When two or more index or new measurable lesions merge without distinct borders between tumors, the smaller lesion should have 0 x 0 mm recorded for the current and all future assessments with a comment indicating that the lesion coalesced with the specified lesion, and the larger lesion should have the size of the merged lesion recorded for the current assessment with a comment indicating that the lesion coalesced with the specified lesion and be followed for future assessments. When two or more nonindex or new non-measurable lesions merge, the smaller lesion should be recorded as absent for the current and all future assessments, and the larger lesion should be recorded as present for the current assessment (with a comment indicating that the lesion coalesced with the specified lesion) and followed for future assessments. If an index or new measurable lesion and a non-index or new non-measurable lesion merge, the non-index or new non-measurable lesion should be absent for the current and all future assessments while the index lesion or new measurable lesion should include both merged lesions for recording measurements with a comment indicating that the lesion coalesced with the specified lesion.

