All other lesions (or sites of disease), including any measurable lesions that were not chosen as index lesions will be identified as nonindex lesions. Nonindex lesions should be recorded and assessed qualitatively over the course of therapy.

Follow-up "Index Lesions":

At each subsequent tumor assessment, the SPD of the index lesions are added together to provide the total tumor burden.

Follow-up "Nonindex Lesions":

Nonindex disease measurements are not required and these lesions should be followed as "present," "absent," or in rare cases "unequivocal progression".

Response Criteria

Evaluation of Objective Response:

The subject response will be assessed based on the response of the index lesions and nonindex lesion, and presence or absence of new lesions. Confirmation of complete or partial response is not required. The overall response is derived from time point response assessments as described in [Table 5](#), [Table 6](#), and [Table 7](#).

Table 5. Definition of Index Lesion Tumor Response Including New Lesions

Complete Response (CR):	Complete disappearance of all index lesions, including any new tumors which might have appeared. Any residual cutaneous or subcutaneous index lesions must be documented by representative biopsy to not contain viable tumor.
Partial Response (PR):	Achieving a 50% or greater reduction in the SPD of the perpendicular diameters of all index lesions at the time of assessment as compared to the sum of the products of the perpendicular diameters of all index lesions at baseline. If any new lesions have appeared, the sum of products of the perpendicular diameters of new measurable lesions must have reduced by 50% or more from when first documented.

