Disease Progression (PD):	
A > 25% increase in the sum of the products of the perpendicular diameters of all index tumors since baseline, or the unequivocal appearance of a new tumor since the last response assessment time point.
 
There are 2 types of PD defined in this protocol:
 
Non-clinically relevant disease progression (PDn): PD in subjects who do not suffer a decline in performance status and/or in the opinion of the investigator do not require alternative therapy. Subjects showing overall response as PDn will be allowed to continue study treatment.
 
Clinically relevant disease progression (PDr): PD that is associated with a decline in performance status and/or in the opinion of the investigator the subject requires alternative therapy. Subjects with PDr will be allowed to remain on study until 24 weeks of therapy unless, in the opinion of the investigator, other treatment is warranted.

Stable Disease (SD):	Neither sufficient tumor shrinkage of index lesion to qualify for response (PR or CR) nor sufficient tumor increase of index lesion to qualify for PD.
Unable to Evaluate (UE):	Any index lesion present at baseline which was not assessed or was unable to be evaluated leading to an inability to determine the status of that particular tumor for that time point.
Not Done (ND)	Radiographic image or clinical measurement were not performed at this time point to evaluate the index lesions

Table 6. Definition of Nonindex Lesion Tumor Response

Complete Response (CR):	Disappearance of all nonindex lesions.
Incomplete Response/Stable Disease (SD):	Persistence of one or more nonindex tumor(s).
Disease Progression (PD):	Unequivocal progression of one or more nonindex lesions There are 2 types of PD defined in this protocol: Non-clinically relevant disease progression (PDn): PD in subjects who do not suffer a decline in performance status and/or in the opinion of the investigator do not require alternative therapy. Subjects showing PDn as overall response will be allowed to continue study treatment. Clinically relevant disease progression (PDr): PD that is associated with a decline in performance status and/or in the opinion of the investigator the subject requires alternative therapy. Subjects with PDr will be allowed to remain on study until 24 weeks of therapy unless, in the opinion of the investigator, other treatment is warranted.

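### The coalescing rule moves tumour area out of or into the index SPD without adjusting the baseline sum, so some merges are recorded as shrinkage or growth that did not occur

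*Protocol*

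**What the plan says.** Two rules in Protocol Appendix D (coalescing lesions) matter here.

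- When two or more "index or new measurable lesions merge without distinct borders between tumors, the smaller lesion should have 0 x 0 mm recorded" at that visit and every later one, and "the larger lesion should have the size of the merged lesion recorded for the current assessment". Index and new measurable lesions form one class, so the larger lesion may be a new one.
- When the partner is a non-index or new non-measurable lesion, the partner is recorded as absent and "the index lesion or new measurable lesion should include both merged lesions for recording measurements".

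Each merge is noted in a comment.

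The comparison itself is fixed. At follow-up, "the SPD of the index lesions are added together to provide the total tumor burden". In Table 5, PR needs the index SPD to be down by half or more "as compared to the sum of the products of the perpendicular diameters of all index lesions at baseline", and any new measurable lesions must also have halved since first recorded. CR needs new tumours to be gone as well. PD is "A > 25% increase in the sum of the products of the perpendicular diameters of all index tumors since baseline"; a tumour that has clearly newly appeared also counts as PD.

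Non-index lesions are those under 10 mm and other non-measurable disease. "This will include any measurable lesions beyond the maximum number of 10 lesions that were not chosen as index lesions". "Nonindex disease measurements are not required", so they have no baseline product.

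No visible text restates the baseline after a merge. The splitting paragraph says that a fragment is not PD on its own; the coalescing paragraph has no counterpart. Protocol 10.2 and 10.4.2 correlate biomarker change with the largest decrease in index lesions, and 10.2 assumes 55 evaluable subjects.

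**The concern.** A percent change from baseline means something only if both sums cover the same tissue. The merge rule changes the current sum and leaves the baseline alone.

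(a) An index lesion absorbed by a larger new measurable lesion leaves the index SPD for good. Tumour has spread or enlarged, and the index sum falls.

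(b) An index lesion that meets a non-index lesion takes in area that was never in the baseline SPD. The index sum rises even if the index lesion is stable or shrinking.

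At stake in (a) are change in tumour burden, the largest index-lesion decrease, and the PD route through index growth. A maximum keeps the most extreme visit, so one artefact can set a subject's value. At stake in (b) is the classification of PD and PR, and so ORR, the outcome of the primary correlation.

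**Working it through.** No sample size or power figure in the plan depends on this rule, so there is no stated figure to reproduce. The check applies the rule to worked lesions.

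**Assumption.** The documents give no lesion sizes. Lesions are taken as squares lying end to end, so a merged lesion measures (sum of sides) x (larger side), in mm.

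**Formula.** Percent change = 100 x (current index SPD / baseline index SPD - 1). Table 5 limits: PR at -50% or lower, PD above +25%.

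**(a) Index lesion absorbed by a larger new lesion**

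- Sole index lesion 15x15 = 225; new lesion 20x20 = 400; merged 35x20 = 700, with no true shrinkage.
- Index SPD: 225 to 0, or -100%.
- New-lesion sum: 100 x (700/400 - 1) = +75%, so PR fails. The new tumour persists, so CR fails.
- The same tissue measured separately is 225 + 400 = 625. The merged 700 is +12% on that, from using one product for two squares.
- With k equal index lesions and one absorbed, the change is 100 x ((k - 1)/k - 1) = -100%/k: -100% (k = 1), -50% (k = 2), -20% (k = 5), -10% (k = 10).
- Masked growth: a sole index lesion going from 15x15 to 18x18 = 324 is +44%, which is PD. Once absorbed it records -100%.
- With k = 2 and one absorbed, the other must exceed 1.25 x 2 = 2.5 times its baseline product before the index sum signals PD.

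**(b) Index lesion merging with a non-index lesion**

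- Sole index 20x20 = 400, unchanged, plus a 5 mm lesion: 25x20 = 500, +25%, not above the limit.
- Plus a 6 mm lesion: 26x20 = 520, +30%, PD.
- Plus a 9 mm lesion: 29x20 = 580, +45%, PD.
- Dilution over k equal index lesions, with a 9 mm partner: 20x20 lesions give 45%/k, above 25% only for k = 1. 10x10 lesions give 90%/k, above 25% for k = 1 to 3.
- With all 10 index places used, a merge with an equal-size non-index lesion adds 100%/10 = 10%, below the limit.
- Hidden PR: 20x20 shrinks to 14x14 = 196 (-51%). Merged with a 9 mm lesion it records 23x14 = 322, or -19.5%, which is SD.
- The distortion lasts. After a 10x10 index lesion merges with a 9 mm lesion (19x10 = 190), PR still needs 50 or less, a shrinkage of 1 - 50/190 = 74% in the merged mass.

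**The case against.** **False responses.** A reader might infer that (a) records a response at the merge. Table 5 does not support that. CR needs the new tumour gone, PR needs the new lesions halved, and the new lesion was already PD when it appeared. A false PR needs the merged mass to be at most half the new lesion's first size. For example, with a 10x10 index lesion unchanged and a new 20x20 shrunk to 10x10, the merged 20x10 = 200 gives index -100% and new -50%. That is a narrow case.

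**Time to treatment failure.** A reader might infer that TTF simply runs on. SAP section 6 also ends it at death, or when alternative or new anti-cancer therapy is needed, and PDr turns on performance status or the investigator's judgement as well as lesion size.

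**Size of (b).** A reader might picture two 10x10 index lesions beside an untouched 10x10 non-index lesion. A lesion of that size is measurable and would ordinarily be an index lesion when fewer than 10 are chosen. The realistic partners are under 10 mm, or lie beyond the 10 index lesions. Lesions that lose their border have usually grown somewhat, and a deep response survives: four 20x20 index lesions each down 60% (160 each), one merged with a 9 mm lesion, give (3 x 160 + 21.65 x 12.65)/1600 = 0.47, or -53%, still PR. A false PD does not by itself bar a later PR. All of this stands, and it confines (b) to subjects with few or small index lesions. The protocol enrols such subjects: inclusion criterion 107 accepts small superficial lesions in aggregate, and Appendix D lets these be index lesions.

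**Reading and redaction.** The first rule could be read as index with index and new with new only. Mixed merges would then have no rule, which also needs repair. SAP 11.4 is partly redacted, so an adjustment there cannot be excluded.

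**Conclusion.** The point stands and should be corrected. As worded, the coalescing rule breaks the comparison of current with baseline index SPD. In (a), which crosses the boundary between index and new lesions, the false fall is 100%/k for k equal index lesions. It damages tumour burden, the largest index-lesion decrease and the detection of later index growth; it does not in general create responses. In (b), which crosses the boundary between index and non-index lesions, a false PD or a hidden PR is possible when index lesions are few or small.

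This rests on the mixed index/new reading of the first rule, on there being no adjustment in the redacted SAP text, and on illustrative lesion sizes. That merging is common is an inference that the documents do not establish. Without a merge frequency, the net effect on ORR or on r cannot be quantified.

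**What to change.** **Index/new merges.** Amend Appendix D so that the merged lesion is always carried under the index lesion, with the new lesion set to 0 x 0, whichever was larger. The cost is wording only. PR becomes stricter after such a merge, because the new lesion's area then counts in the index sum; the +25% limit is reached sooner for the same reason. The effect is small with several index lesions and larger with one, but the added area is real tumour that arose after baseline.

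**Index/non-index merges.** Use the existing merge comments to flag affected subjects. Repeat the ORR and largest-decrease analyses with merged lesions excluded from both the baseline and the follow-up SPD. Report how many subjects are affected, and how many have no index lesion left. This needs one derivation step and no new measurements.

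**What to avoid.** Do not add the jump at the merge visit to the baseline. Suppose a 20x20 index lesion grows to 30x30 while merging with a 5 mm lesion: merged 35x30 = 1050, and the jump is 1050 - 400 = 650. The new baseline would be 1050, so true growth reads 0%. Later shrinkage to 525 would score as PR, although the true baseline was 400, or 400 + 25 = 425 with both lesions.

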Another secondary objective is to explore the correlation between changes in intratumoral CD8+ cell density during treatment and objective response rate. The primary focus will be on changes in tumor cell CD8+ density. It is assumed that 55 subjects (approximately 50% of all enrolled) will be evaluable with a pre- and on-treatment lesion biopsy that is sufficient to evaluate biomarker changes in uninjected lesions. In addition to correlating biomarker changes with objective response, Pearson's correlation coefficient (r) will also be estimated between the biomarker change and the maximum decrease in index lesions. With 55 evaluable subjects, a value of $r \leq 0.30$ will be rejected at a nominal 1-sided 5% significance level with an observed $r > 0.49$ for which the power will be $> 80\%$ given a true value for $r \geq 0.60$.

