- **Splitting lesions:** When an index or new measurable lesion splits into two or more lesions the largest measurable part of the split lesion should be considered to be the previously recorded index or new measurable lesion with measurements provided for the current assessment with the comment indicating that the lesion split from the specified lesion, and followed for future assessments. The remaining lesions would be reported as a new measurable lesions or new non-measurable lesions depending on measurability with a comment indicating that the lesion split from the specified lesion. In this case, appearance of a new lesion from a previous lesion will not be considered a disease progression solely due to appearance of a new lesion (may be considered a disease progression due to > 25% increase in the sum of the products of the perpendicular diameters of all index tumors since baseline, or the unequivocal appearance of a new tumor, other than the product of the split tumor, since the last response assessment time point).

Measurable Tumor Assessment/Burden:

Baseline Documentation of “Index Lesions”:

All baseline evaluations should be performed as close as possible to enrollment and never more than 4 weeks (ie, 28 days) prior to enrollment.

At baseline, up to 10 measurable cutaneous, nodal, or soft tissue lesions will be chosen to measure over the course of therapy. The distribution of these index lesions should be representative of the subject's overall disease status. Index lesions should be selected on the basis of their size (lesions with longest bi-dimensionally perpendicular diameters) and suitability for accurate repeated measurements by imaging techniques (CT, MRI or ultrasound) and/or other method such as clinical exam.

The sum of the products of the two largest of perpendicular diameters (SPD) of all index lesions will be calculated and reported.

If subject has multiple small superficial melanoma lesions at baseline (less than 10 mm in longest diameter) which in aggregate have a total diameter of ≥ 10 mm, up to 10 largest lesions that were included in this measurement will be reported as "Index Lesions", and sum of the products of the two largest of perpendicular SPD of these lesions will be calculated and reported for tumor response assessments.

Baseline Documentation of "Nonindex Lesions":

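### When an index lesion splits, only its largest part stays in the index sum: a split without shrinkage is recorded as a fall in tumour burden, and growth of a measurable fragment meets no stated progression criterion

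*Protocol*

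**What the plan says.** Protocol Appendix D (coalescing or splitting lesions) sets three rules for a split:

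- "the largest measurable part of the split lesion should be considered to be the previously recorded index or new measurable lesion".
- "The remaining lesions would be reported as a new measurable lesions or new non-measurable lesions depending on measurability".
- "appearance of a new lesion from a previous lesion will not be considered a disease progression solely due to appearance of a new lesion". The new-tumour route to progression is limited to "the unequivocal appearance of a new tumor, other than the product of the split tumor".

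At each follow-up, "the SPD of the index lesions are added together to provide the total tumor burden". Nothing adjusts the baseline sum after a split.

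Table 5 applies its thresholds to the same index sum. Progression is "A > 25% increase in the sum of the products of the perpendicular diameters of all index tumors since baseline", or a new tumour. Partial response (PR) is "Achieving a 50% or greater reduction in the SPD of the perpendicular diameters of all index lesions at the time of assessment", with the further condition that the summed products of any new measurable lesions have halved since first recorded. Complete response (CR) requires every new tumour to be gone. No confirmation of response is needed.

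The coalescing rule works differently: when lesions merge, the larger one takes the size of the merged lesion, so the tissue is carried forward.

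Protocol Section 10.1.1.2 lists change in tumour burden as a secondary endpoint. Sections 10.2, 10.4 and 10.4.2 plan Pearson's r between biomarker change and "the maximum decrease in index lesions".

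**The concern.** After a split, the numerator of the burden change loses tissue that the denominator still contains. The recorded value falls although nothing has regressed. A maximum-decrease outcome then keeps that value for good if it is the lowest one recorded.

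The relabelled fragment also drops out of the progression criteria. It is no longer in the index sum, and its appearance is expressly not progression. At stake are the values of two secondary outcomes and the timing of progression.

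**Working it through.** The plan states no figure that depends on this rule, so there is nothing to reproduce. The check applies the written rule to illustrative splits. Lesion sizes are assumptions, because the documents give none. A split without shrinkage means that the fragments' products of diameters sum to the parent's product.

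**Recorded change at the split.** Let w be the lesion's share of the baseline index sum and q the share of its product kept by the largest part. Recorded change = -w(1 - q); true change = 0.

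| Case | Calculation | Recorded | True |
|---|---|---|---|
| One lesion, 40x20 mm into two 20x20 | 400/800 - 1 | -50% | 0% |
| One lesion, 50x20 into 30x20 and 20x20 | 600/1000 - 1 | -40% | 0% |
| One lesion, 60x20 into three 20x20 | 400/1200 - 1 | -66.7% | 0% |
| Two equal lesions, one equal split | 1.5/2 - 1 | -25% | 0% |
| Five equal lesions, one equal split | 4.5/5 - 1 | -10% | 0% |
| Ten equal lesions, one equal split | 9.5/10 - 1 | -5% | 0% |

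Ten is the maximum number of index lesions in Appendix D.

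**Later growth of the dropped part.** In the first case, let the dropped 20x20 fragment grow to 30x30 while the retained part is stable. The index sum stays at 400/800, or -50%. The true total is (400 + 900)/800 - 1 = +62.5%. Taking the progression routes in turn:

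- Index sum: the fragment is not in it.
- New tumour: split products are excluded.
- Nonindex progression (Table 6): this covers lesions documented at baseline, since the table's not-applicable category is for subjects with none at baseline.

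A measurable fragment therefore meets none of them. For fragments under 10 mm the text is ambiguous. The nonmeasurable-lesion paragraph classes all small lesions as nonindex, while the coalescing rule lists new non-measurable lesions separately from nonindex ones.

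If all fragments grow at the same rate and the split lesion is the only index lesion, tissue must reach 1.25/q times baseline before index progression: 1.56 times at q = 80%, 2.08 at 60%, 2.5 at 50%. Without a split the factor is 1.25.

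**Response.** In the 50/50 case the index sum meets the 50% threshold, but the measurable fragment blocks PR until it has halved, and any fragment blocks CR. The guard has two faults:

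- It can refuse a true PR. Let 40x20 split equally, the index half vanish and the other half shrink to 20x12. The true total is 240/800 - 1 = -70%. The new lesion has fallen only 240/400 - 1 = -40%, so PR is not met.
- It does not cover small fragments. On the longest-diameter definition of measurability, let 20x9 split into 10x9 and two 9x5. The index sum goes from 180 to 90, or -50%. The fragments total 180, so nothing has shrunk. Both dropped parts are under 10 mm, so the new-measurable condition has nothing to test.

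**The case against.** The strongest reply concerns reach, and much of it stands.

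- A reader might infer that splitting inflates the objective response rate. The documents do not support that. A false PR needs dropped fragments under 10 mm together with an exact half, a multi-way split or some real shrinkage, and the guard can also withhold a true PR.
- A reader might infer a material delay in time to treatment failure. SAP Section 6 still counts death and the start of new anticancer therapy. Non-clinically relevant progression without a need for other therapy would not have counted anyway. What remains is mainly clinically relevant progression not yet followed by new therapy.
- A reader might infer that Pearson's r is pushed upward. Error unrelated to CD8 change would ordinarily weaken r. Inflation would need splitting to track CD8 change, which the documents do not address. That splitting is commoner in treated lesions is also inference, and if it is, part of the recorded fall may be real.
- The effect shrinks as the number of index lesions grows, and parts of SAP Sections 6 and 11.4 are redacted, so a derivation for tumour burden could lie there.
- Summing fragments could be said to loosen PR. With a 60/40 split, let the index part fall from 60 to 20 and the fragment from 40 to 30. PR is refused now and granted under the sum. But 100 to 50 is a true 50% fall, so that call would be correct.

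None of this removes the core: the visible rule gives a wrong burden value after a split and leaves growth of a measurable fragment outside every progression criterion.

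**Conclusion.** The point holds as a defect in a measurement rule. Because fragments have non-negative products, the recorded burden after an index-lesion split can never exceed the total across fragments, so the error in the burden value itself runs one way. Its size per affected subject is w(1 - q): up to 40% to 50% for a single index lesion in a two-way split of the kind shown, and 5% for one equal split among ten equal lesions.

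It affects two secondary, descriptive outcomes, and it leaves a gap in progression for measurable fragments. The effect on the study's results cannot be estimated, because the frequency of splitting is unknown. The conclusion rests on the literal protocol text and on the visible SAP containing no correcting derivation. It does not extend to a general inflation of response, a large effect on time to treatment failure, or a known direction of bias in r.

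**What to change.** In Appendix D, state that after a split the value for the parent lesion, whether index or new measurable, is the sum of the products of diameters of all its fragments, and that fragments are not new lesions for Table 5. Align the new-lesion wording in Table 5. In the SAP, derive the index sum, the maximum decrease, PR and the >25% progression test from that value. This is a measurement rule only; the treatment-stopping rules are untouched. It brings splitting into line with the coalescing rule.

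The cost is small. Fragments are already tied to the parent lesion by the required comment, and measurable new lesions already need their products for the PR rule. The downsides are that fragments under 10 mm must be measured, and that the separate fragment-level PR condition no longer applies to split products, so some PR calls will change in either direction to match the true total. Reporting the number of subjects with a split would show how much the rule matters.
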